8.4 Screening post consent

An inclusion criterion is the presence of sarcopenia which is determined by the presence of low muscle strength measured using a hand grip dynamometer (<27kg men and <16kg women). This will be determined after the participant has given consent. If their hand grip strength is found to be below these cut off thresholds, they will be eligible to take part in the study and will be randomised. If their hand grip strength is above these cut off thresholds, they are ineligible and will not be randomised.

As part of the Patient and Public Involvement work that we carried out prior to grant submission, patients suggested to include an opportunity to try the NMES procedure before they are randomised to see how well they are able to tolerate it. For those patients that are eligible, they will be offered the opportunity to try NMES on one occasion. The researcher will talk them through the procedure and explain which parameters will be changed and give the opportunity to control the different parameters to see how they find it. If patients do not think they will be able to tolerate the NMES they can withdraw from the study before they are randomised. As part of the screening visit, we will also familiarise people with the isometric strength measurement, our primary outcome measurement. This is to ensure they are able to complete this assessment with no problem and to eliminate any learning effects in the assessment visit.

8.5 Additional consent provisions for collection and use of participant data and biological specimens in ancillary studies

Not applicable for this study.

8.6 Randomisation

After consent and baseline measurements have been collected, participants will be randomised by a delegated individual at each participating centre to either the intervention (3-months of NMES) or the control group (standard care) in a 1:1 manner. Participants will be allocated using minimisation factors of age and time on dialysis, this will ensure the external validity of the results.

Each participant will be given a unique participant ID number at randomisation. This participant ID number will be used to identify the individual participant throughout the study and will not be re-assigned to any other participant. Due to the nature of the intervention, blinding of the participants and the study team to the randomisation arm is not possible.

Randomisation will be performed using a validated web-based system to maintain allocation concealment. This will be managed by the Leicester Clinical Trials Unit.

8.7 Baseline data

These assessments can be split over multiple visits if the participant wishes.

1) Demographic and clinical information:

Date of birth/age, gender at birth, ethnicity, medical history and medications will be collected from hospital records.

2) Hand Grip Strength

Participants will perform this assessment seated with their feet flat on the floor, or standing if participant cannot be seated using the non-fistula arm. Participants will be asked to squeeze the handheld dynamometer as hard as they can on three occasions with a short rest in between. The highest measurement will be taken.

3) Isometric strength and rate of force development

Participants will be seated in a custom-built dynamometer, with their lower leg secured to a brace in series with a strain gauge force transducer. Following a series of warm-up contractions of gradually increasing force, participants will perform a series of 3-4 brief maximum voluntary contractions lasting ~5 s and separated by ~1 minute of rest, attempting to exert as much force as possible during each contraction. After that, participants will perform 10 efforts of contracting "as fast and as hard as possible" for ~1 s to at least 80% of maximal force (separated by 30-45 seconds of rest) to allow assessments of the rate of force development.

4) Quadriceps Cross-sectional area and architecture

Measures will be taken at mid-point of the thigh, and three measures (within 10%) of rectus femoris cross sectional area will be taken and the mean recorded. Three measures of muscle thickness will be taken and the mean recorded. Images of the quadriceps will be taken (pseudonymised) for later analysis of grayscale (muscle quality). Muscle thickness and angle of pennation will also be measured by ultrasound at points along the quadricep.

5) Short Physical Performance Battery

This involves 3 successive balance tests, side by side stand, semi tandem stand, and full tandem stand, a gait speed test and sit to stand 5 test.

Balance tests

The participant is asked to stand unsupported for 10 seconds with their feet in a certain position (feet together, semi tandem, full tandem). The length of time they are able to remain balanced for in seconds is recorded.

Figure 2: Image of three foot positions during the balance tests

Gait Speed

The participant walks between two timing gates or cones at their usual walking pace placed 4m apart. Speed in m/s is recorded.

Sit to Stand 5 test

The participant starts from a seated position on a hard, upright chair (such as a dining chair), with the feet flat on the floor and the knees bent at 90°. For the test, the participant simply stands up fully and then sits down again to the starting position, without using the hands (one cycle). The length of time in seconds that it takes for the individual to complete 5 repetitions is recorded.

6) Sit to Stand 60 test

The participant starts from a seated position on a hard, upright chair (such as a dining chair), with the feet flat on the floor and the knees bent at 90°. For the test, the participant simply stands up fully and then sits down again to the starting position, without using the hands (one cycle). The number of cycles achieved in 60 seconds will be recorded to provide a surrogate measure of muscular endurance.

7) Six-minute walk test

Cones are placed up to 10-30m apart (depending upon space available) and the individual is asked to walk as far as they can in 6 minutes. Distance walked in meters is recorded.

8) Incremental shuttle walk test (ISWT)

The participant walks a level 10m shuttle course at a speed controlled by an external audible bleep signal. The bleep speed progressively increases at 1 minute intervals for a total of 12 stages, and the test is terminated when the participant fails to complete the shuttle course in the allowed time, or reaches volitional exhaustion. We may also ask participants to wear the accelerometer during this test (see section below on accelerometry).

9) Bioelectric Impedance Analysis (BIA)

BIA analysis will be carried out using a free-standing BIA monitor. This is a painless, non-invasive method for measuring fat and fat free mass. Participants will stand on the monitor platform in bare feet and grip the handles firmly while the monitor takes the measurement. The procedure takes around two minutes.

10) Accelerometry

Participants will be asked to wear an accelerometer on their non-dominant wrist for 24 hours/day for 8 days. The participant does not have to do anything with the device apart from wearing it, and once it is fitted on the day of the appointment, it will not need to be removed until the wear period is over. Participants will be asked to return the watch at their next study appointment or hospital visit. Data captured by these devices will allow assessment of physical activity levels and patterns, sedentary time and sleep. Participants will also complete sleep diary over the course of 8 days to complement the data from the accelerometer. Using the diary, participants will record the time they went to sleep, and the time they woke up. Naps will not be recorded. Participants will be given two instructions documents; one containing accelerometer wear instructions and another containing instructions for completing the sleep diary.

11) Questionnaires

Participants will be asked to complete the Kidney Disease Quality of life Tool (KDQoL), EQ-5D-5L questionnaire, SONG-HD questionnaire, the SARC-F questionnaire, GP Physical Activity questionnaire, the SarQoL questionnaire and a resource use questionnaire, which will be combined into one survey pack. The EQ-5D-5L and resource use questionnaire will capture the data needed to perform the health economic evaluation. To minimise recall bias, participants will be offered a resource use diary in which to record their healthcare visits and other related resource use and expenditure to aid completion of the aforementioned self-completed questionnaire. This will be optional.

12) Blood sample:

Up to 40ml (approximately 3 tablespoons) venous blood sample will be taken from the arterial dialysis line within the first hour of dialysis. Plasma/serum will be separated and stored at -80°C before the analyses described below.

Samples will be analysed/used for some or all of the following:

- Markers of metabolism and homeostasis
- Inflammatory markers and immune cell function/activation
- Biomarkers of cardiovascular risk
- Endothelial damage

- Oxidative stress
- Anabolic/catabolic hormones
- microRNA and full RNA expression
- Small extracellular vesicles isolation (exosome/microparticle)
- Genetic analysis (with relevant clause in the consent form)
- Pre-conditioning of cells in vitro
- Isolation of peripheral blood mononuclear cells (PBMCs)

8.8 Work Package 4: Optional mechanistic study

Optional mechanistic outcomes will be performed in a sub-group (both study arms) to assess the mechanistic effects of neuromuscular electrical stimulation on skeletal muscle morphology and function in haemodialysis patients. Participants will indicate via the consent form whether or not they wish to participate in the following optional assessments. Participants can still take part in the main study without completing these assessments. These assessments will be performed in centres with appropriate capability and capacity, at baseline and at 3-month follow-up only. These are optional procedures and will only be done in some centres.

1. Skeletal muscle biopsy using the needle biopsy procedure

The number of biopsies that we will take will depend upon which group participants are randomised to. We will collect three samples from the NMES group, and two samples from the Control group:

- NMES group sample 1: Taken at baseline in the days prior to the first NMES session
- NMES group sample 2: Taken 24 hours after the first NMES session. This will provide crucial information on how the muscle has responded to the intervention
- NMES group sample 3: Taken 24 hours after the last NMES session. This will provide crucial information on how the training period has affected the muscles response to the intervention.
- Control group sample 1: Taken at baseline in the days before the start of the 3-month period
- Control group sample 2: Taken in the days at the end of the 3-month period.

Participants will be asked to refrain from eating or drinking anything other than water on the morning of the biopsy. A biopsy sample will be collected using the needle biopsy technique.

A muscle biopsy of the vastus lateralis (quadriceps), or another appropriate muscle will be taken using the needle biopsy procedure. With the participant lying supine, the skin of the thigh is sterilised using either chlorhexidine or iodine solution and anaesthetised using 1% lidocaine injected subcutaneously as local anaesthetic. A small incision (<0.5cm) is then made through the skin, subcutaneous fat and muscle fascia at a mid-thigh and lateral position. Through this incision a 12-guage single use microbiopsy needle is inserted and a small sample of muscle (approx. 100mg) taken. Depending upon the amount of tissue collected additional passes may be required at the same site using the same incision. A steristrip and a bandage are then applied. The whole procedure takes about 15 minutes, and has been used successfully in our previous studies, which was well-tolerated (ExTra CKD ref 13/EM/0344, Explore CKD Ref 15/EM/0467). The administration of local anaesthetic may cause mild discomfort, and there is a small risk of haemorrhage or infection at the site of the biopsy. Following the local anaesthetic, the procedure is not painful, though the site of the biopsy may ache for a day. Analgesia will be offered following the procedure. All biopsies will be performed by trained healthcare professional and had experience of the procedure.

The muscle samples will be analysed for some or all of the following:

- Markers of metabolism and homeostasis
- Muscle morphology/anatomical structure/fibre type
- Protein turnover (protein synthesis and degradation) and events leading to this
- The process of myogenesis (muscle repair and regeneration)
- Neuromuscular function
- Intramuscular inflammation and processes relating to this
- Mitochondria number/function and processes relating to this
- Amino acid content and transport
- RNA and microRNA expression
- 2. Surface Electromyography (EMG)

Following preparation of the skin, high density grid electrodes will be placed over the surface of the thigh muscles,

prior to the following voluntary muscle contractions below. The EMG grid facilitates recording of muscle electrical activity and subsequent decomposition enables the behavior (recruitment and discharge rate) of individual motor units to be discerned. This technique has been used several times before in clinical populations with no adverse effects (IRAS ID's: 22569, 306712, 321959). Using the same dynamometer as for the isometric strength exercise, participants will complete a series of gradual sub-maximum contractions, by following a target line on the screen to achieve specific sub-maximum contraction levels.

3. Intramuscular Electromyography

The needle insertion location over the vastus lateralis muscle will be identified and cleansed, before insertion of a 26-gauge needle into the leg, ~20-40mm below the surface and into the vastus lateralis muscle. Then whilst the participant is sat on the same isometric dynamometer, participants will complete a further series of low-level gradual sub-maximum contractions.

4. Femoral nerve stimulation

Electrodes will be placed in the femoral triangle just medial of the inguinal ligament and at the top of the femur in order to evoke contractions in response to percutaneous stimulation of the femoral nerve. With participants seated on the same isometric dynamometer, the intensity of stimulation of the femoral nerve will be individualised by gradually increasing the current until a plateau in the evoked twitch response is detected (or the individual's tolerance level is reached, whichever occurs sooner). Then three identical measurement stimulations will be delivered at rest, separated by ~15-20 seconds.

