8.9 Neuromuscular electrical stimulation (NMES)

Participants randomised to the NMES group will receive NMES at each dialysis session they attend for 3-months. It will be administered using a commercially available 4-channel portable stimulator with participants either sitting or laid down (however they are usually positioned for dialysis). The skin will be cleaned and then electrodes will be placed upon the thigh muscles. The participants will have control of the NMES device on which they will be able to change the current that is administered. During the first two to three sessions participants will be encouraged to find their initial comfortable level of stimulation intensity (the current) and to get used to how it feels. After the first week the training will be progressed by two methods:

- 1. Increasing session duration up to a maximum of 30 minutes, if this is not initially achievable (excluding warm up and cool down)
- 2. Increasing stimulation intensity (current) which determines the strength of the muscle contraction that is induced and therefore how uncomfortable it can feel.

Participants will be encouraged to increase the stimulation intensity beyond their initial comfortable level for a portion of each session. As participants become increasingly familiar with NMES and as they adapt they will be encouraged to progressively increase the stimulation intensity further. This progression will also be guided by their individual rating of perceived exertion (RPE). RPE is a scale that guides exercise intensity. Participants will be familiarised with this in the first few NMES sessions. Participants will be encouraged to achieve a of about '4' or 'somewhat' hard. In addition, a discomfort scale will be shown to the participants to help ensure the stimulation intensity is at the correct level. Exercise intensity will also be monitored through a session using a heart rate monitor to measure heart rate and blood lactate concentrations will be measured at the end of the session. Both of these will be performed once a month to more closely monitor progress.

Heart rate monitor: A heart rate strap will be placed around the middle of the chest and a watch placed on the participants wrist to measure heart rate over the course of the NMES session.

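### Optional biopsy substudy: the 7.1 footnote implies four NMES biopsies where 8.8 and the 7.1 table give three, and at 3 months only the NMES biopsy is tied to a dialysis session

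*Protocol*

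**What the plan says.** All references are to the main STIM-HD trial in the Protocol.

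**Number of biopsies.** Section 8.8 states: "We will collect three samples from the NMES group, and two samples from the Control group". It then lists them one by one. The biopsy row of the 7.1 schedule for the NMES group shows 2 at baseline and 1 at 3 months. The footnote to the same table says that the NMES group has an additional biopsy following the first training session, and places it at baseline and at 3 months alike.

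**Timing in the NMES arm (8.8).** The opening biopsy has no fixed hour or session: "NMES group sample 1: Taken at baseline in the days prior to the first NMES session". The next one is pinned to the start of stimulation: "NMES group sample 2: Taken 24 hours after the first NMES session". The final one is pinned to the end of the programme: "NMES group sample 3: Taken 24 hours after the last NMES session".

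**Timing in the control arm (8.8).** The opening biopsy is again loosely placed: "Control group sample 1: Taken at baseline in the days before the start of the 3-month period". The closing biopsy, which is the comparator at 3 months, is placed just as loosely: "Control group sample 2: Taken in the days at the end of the 3-month period".

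**Link to dialysis.** Section 8.9 says that NMES participants "will receive NMES at each dialysis session they attend for 3-months".

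**Use of the data.** Section 3.3.2 lists skeletal muscle biopsy analysis among the secondary endpoints to be compared between the randomised groups. Section 11.3.4 applies regression adjusted for the baseline value to the secondary outcomes. For sample 3, section 8.8 gives its own purpose: "This will provide crucial information on how the training period has affected the muscles response to the intervention".

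**The concern.** There are two separate matters.

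First, the schedule table is what a site works from when it books procedures. Its footnote disagrees with the row it annotates and with 8.8 on how many biopsies an NMES participant has at 3 months. The procedure is invasive, and the Protocol itself states a small risk of haemorrhage or infection (8.8, 10.3 and 14.4). Site instructions and consent should rest on one number.

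Secondly, the 3-month biopsies of the two arms are timed by different rules. The NMES sample is pinned to a session that takes place at dialysis; the control sample can fall anywhere in the days around the end of the period. If a muscle readout changes between dialysis sessions, part of the 3-month difference between arms would reflect time since dialysis rather than NMES. Adjusting for baseline does not remove a timing difference that arises at 3 months. It can be prevented only through the way visits are booked, before tissue is taken.

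**Working it through.** **1. Count of biopsies**

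Inputs: 12 participants per arm (section 4 and the study summary); NMES 3 and control 2 (8.8); 2 + 1 (7.1 row); one additional biopsy at each of two time points (7.1 footnote).

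| Source | Per NMES participant | NMES arm | Control arm | Total |
|---|---|---|---|---|
| 8.8 list | 3 | 12 × 3 = 36 | 12 × 2 = 24 | 60 |
| 7.1 table row | 2 + 1 = 3 | 36 | 24 | 60 |
| 7.1 footnote, literal | (1 + 1) + (1 + 1) = 4 | 12 × 4 = 48 | 24 | 72 |

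The plan's stated figure of three reproduces from both the list and the table row. The footnote exceeds it by one per NMES participant, or 72 − 60 = 12 overall. It also cannot be carried out at 3 months, because the biopsy due then follows the last session, not the first.

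**2. Timing of each sample relative to dialysis**

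| Sample | Rule in 8.8 | Time since dialysis |
|---|---|---|
| NMES 1 | days before first NMES session | not set |
| NMES 2 | 24 hours after first NMES session | about one day |
| NMES 3 | 24 hours after last NMES session | about one day |
| Control 1 | days before the period starts | not set |
| Control 2 | days at the end of the period | not set |

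The entry of about one day combines 8.8 with 8.9. It is an inference and is nominal: the Protocol fixes neither the length nor the frequency of dialysis, home patients are eligible, and 14.4 schedules needle biopsies for the morning, fasted. Section 7 asks for 3-month assessments within two weeks of the end of the intervention or standard care period where possible, which does not narrow the control timing to any session.

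What this means for each contrast:
- NMES 3 against control 2 (between arms): timing is unmatched, so time since dialysis can enter the difference.
- NMES 3 against NMES 2 (within arm): both are 24 hours after a session, so it is matched and unaffected. This contrast serves the purpose 8.8 gives for sample 3.
- NMES 3 against NMES 1 (within arm): unmatched.
- Sample 1 between arms: equally loose in both arms, so it adds noise rather than a systematic difference.

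**3. Possible size**

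Suppose a share s_k of control samples is taken at timing k, and a readout at that timing differs by d_k SD from its value about one day after dialysis. The arm difference then shifts in magnitude by |Σ s_k × d_k|. The d_k may be positive or negative and may differ between a dialysis day, the second day and later days. The documents give neither the s_k nor the d_k, so no figure or bound can be derived. The shift is zero if controls are sampled about one day after dialysis, or if every d_k is zero.

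For scale only: the standard error of an unadjusted 12 v 12 mean difference is √(2/12) = 0.408 SD. With t(0.975, 22 df) = 2.074, the 95% confidence interval half-width is 2.074 × 0.408 = 0.85 SD. Only a large shift would be visible against that.

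**The case against.** The case on the other side is substantial.

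- **No harm is shown.** Nothing in the documents says that a muscle readout changes with time since dialysis. This stands, and it is why the timing part is a cheap improvement and not a demonstrated bias.
- **The 24-hour rule is deliberate.** It makes samples 2 and 3 comparable within the NMES arm. This stands. Sample 3 also carries the acute effect of the last NMES session, and matching the control biopsy to dialysis leaves that effect in the arm contrast.
- **Loose timing of sample 1.** A reader might infer that it biases the comparison between arms. The wording is equally loose in both arms, so the documents do not support that; it bears mainly on noise and on the NMES change from sample 1 to sample 3.
- **The footnote is a slip.** Two explicit statements agree on three, so a reader who infers that 12 extra biopsies will in fact be taken goes too far. A lenient reading (a post-session biopsy at each time point, three in all) is possible, but it strains the sense of an additional biopsy at 3 months and still attaches that biopsy to the wrong session. As an instruction on an invasive procedure it needs correcting.
- **Booking is not free.** Research blood is drawn from the dialysis line during a session, which does not show that a separate fasted morning visit is easy. Section 7 also lets participants split visits as they wish. The constraint is real but small.

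**Conclusion.** Both parts hold at minor weight, within an optional substudy of 24 participants.

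The footnote is wrong as written. It implies four NMES biopsies instead of three, or 48 instead of 36 in the arm, and names a session that does not exist at 3 months. This rests on the text alone.

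The timing asymmetry is also in the text, given one inference: NMES is delivered at dialysis, so 24 hours after NMES is about one day after dialysis. The 3-month comparison between arms can therefore mix NMES with time since dialysis. A reader might go further and conclude that the comparison is biased, or that matching would isolate the training effect. The documents support neither: the size and direction of any bias are unknown and may be zero, and the acute effect of the last session remains by design. The sample 2 v sample 3 contrast in the NMES arm is sound as planned.

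**What to change.** 1. **7.1 footnote.** State that the additional NMES biopsy is taken 24 hours after the first session, at baseline only, and that there is a single 3-month biopsy, 24 hours after the last session. Cost: wording only.
2. **8.8, control sample 2.** Book it about 24 hours after a dialysis session at the end of the 3-month period, keeping the existing fasting rule. Cost: a small scheduling constraint for the 12 control participants; no extra biopsies.
3. **CRF.** Record hours since last dialysis for every biopsy in both arms, so that any remaining imbalance can be seen. Cost: one field.
4. **Optional.** Anchor sample 1 in both arms in the same way. This would reduce noise and make the NMES change from sample 1 to sample 3 easier to read, but the between-arm comparison does not depend on it.

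The report should also say that the 3-month arm contrast includes the acute response to the last NMES session.
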